#### Re-screening

It is permitted to re-screen subjects, if the reason for non-eligibility is considered transient to the investigator's opinion. During a re-screening, only assessments that are susceptible to change within the timeframe between screenings are repeated (e.g. medical history, demographics, virology are not repeated).

In addition, retests are permitted in case false-positives are expected and adequately documented by the investigator (e.g. positive drug screen due to accidental poppy seed consumption).

#### Treatment and observation period

The overview of all assessments including time schedule is provided in the study flow chart (Table 1). Subjects will present to the CRU in the afternoon of Day -1 (i.e., the day before the study treatment administration) for baseline procedures conducted prior to dosing. Baseline procedures will be performed prior to dosing and study procedures after dosing. Subjects will be discharged in the afternoon of Day 2, approximately 24 hours post-dose.

#### Follow-up

Follow-up will occur between 7 and 14 days after the last study drug administration. The overview of the assessments of this visit is provided in the study flow chart (Table 1). End of Study (EOS) is defined as the last visit of the last subject. Upon early termination, the follow-up visit will also be performed between 7 and 14 days after the last study drug administration.

#### 2.5.2 Number of patients

A total of 24 subjects is planned to be enrolled. All subjects will participate in four study occasions.

#### 2.5.3 Overall study duration and follow-up

The total duration of the study for each subject will be approximately 82 days divided as follows:

- 1. Screening: Up to 42 days before dosing;
- 2. Four identical In Clinic periods; each: Days -1 to 2; washout of at least 7 days between each dosing;
- 3. Follow-up visit: 7 to 10 days after last dose.

Subjects will be admitted to the study unit on Day -1 and will be discharged in the afternoon of day 2.

#### 2.6 STUDY POPULATION

#### 2.6.1 Population

For this study, a total of 24 patients with chronic neuropathic pains, male and female subjects, aged between 18 and 65 years of age (inclusive) will be enrolled.

Subject recruitment to be determined.

#### 2.6.2 Inclusion criteria

- 1. Patient with chronic neuropathic pains, 18 to 65 years of age, inclusive. The patient's ability to be included will be determined following a detailed medical and surgical history, a complete physical examination including vital signs, 12-lead ECG, haematology, blood chemistry, and urinalysis.
- 2. Current treatment of their chronic pain with an opioidergic-acting drug (along with possible other drugs).
- 3. Body mass index (BMI) between 18 and 30 kg/m2, inclusive, and with a minimum weight of 50 kg and a maximum weight of 100 kg.
- 4. Able to participate and willing to give written informed consent and to comply with the study restrictions.
- 5. Normal laboratory assessment of renal and hepatic function (assessed using available clinical biological tests).

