The measurement techniques performed in this study (PainCart® and CNS tests) are considered to be safe and with minimal risk. Capsaicin application on the volar forearm may cause some transient skin irritation on the application site. The skin may become red and/or more sensitive to e.g., warm water, and to touch (a slight burning sensation). After one or two days the effects will generally resolve.

**Table 1.** Visit and Assessment Schedule

	SCR		Treatment period 1 - 4 								FU 						
	SCR	Day -1						С	Day 1							Day 2	
Time point Assessment	Up to -42 d to -5 days	Day -1	Pre- dose	0 h	1h	2 h	3 h	3.5 h	4 h	5 h	6 h	6.5 h	7.5 h	8 h	9 h	24 h	+14 d ± 2 d
Informed consent	Х																
Demography	х																
Inclusion and exclusion criteria	х		х														
Medical history	х																
Height, Weight³, BMI	х																Х
Admission to clinic		Х															
Physical examination 	х		X 														Х
Virology	х																
BsHaem, BsChem, BsGluc, Urinalysis	х	х															Х
UrDrug, BrAlc, UrPreg 	х	Х															Х
Temperature	х	Х	Х													Х	Х
ECG	х		Х											х		х	Х
General symptoms	х		Х		х	х				х				х		х	
Vital Signs (Pulse Rate, BP, RR, O 2 saturation) 			х							х		Х		х		х	Х
Meals / snack 			X8		х				х					х	х	х	
Drug (-placebo) administration				х		х				х							
PK sample			Х		х	X 9			х	X 9	х			х		х	
Capsaicin application	X 		X 														
Capsaicin task – Von Frey test 			х		х		х		Х		х		Х		Х		
PainCart®12,13	X 		X 		Х		Х		Х		Х		Х		Х		
NeuroCart®12	X 		X 		х	х		х		х		Х			х		
pEEG			X 			Х				Х		Х			Х		

VVLT 	х					х			Х					
STAI	х		х		х	х		Х	Х	Х		Х		
BSI		Х										Х		
Discharge	Х												X 	
(S)AE			continuous						Х					
Concomitant medication	Х		continuous						Х					

BP = Blood Pressure, HR = Heart Rate, RR = Respiratory Rate, SCR = Screening, EEG = Electroencephalogram, PK = Pharmacokinetics, AE = Adverse Event, (S)AE = Serious Adverse Event, UrDrug = Urine Drug Screen, UrPreg = Urine Pregnancy test, BsHaem = Blood Sample Haematology, BsChem = Blood Sample Chemistry, BsGluc = Blood Sample Glucose, BsBiomarker = Blood Sample Biomarker, BrAlc = Breath Alcohol Test., BMI = Body Mass Index

- At least 7 days between treatment periods

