#### 2.6.3 Exclusion criteria

- Evidence of any active or chronic disease or condition that could interfere with, or for which the
  treatment of might interfere with, the conduct of the study, or that would pose an unacceptable
  risk to the subject in the opinion of the investigator (following a detailed medical history, physical
  examination, vital signs (systolic and diastolic blood pressure, pulse rate, body temperature) and
  12-lead electrocardiogram (ECG)). Minor deviations from the normal range may be accepted, if
  judged by the Investigator to have no clinical relevance.
- 2. Clinically significant abnormalities, as judged by the investigator, in laboratory test results (including hepatic and renal panels, complete blood count, chemistry panel and urinalysis). In the case of uncertain or questionable results, tests performed during screening may be repeated before randomization to confirm eligibility or judged to be clinically irrelevant for patient with chronic neuropathic pains.
- 3. Positive Hepatitis B surface antigen (HBsAg), Hepatitis C antibody (HCV Ab), or human immunodeficiency virus antibody (HIV Ab) at screening.
- 4. Systolic blood pressure (SBP) greater than 140 or less than 90 mm Hg, and diastolic blood pressure (DBP) greater than 90 or less than 50 mm Hg at screening.
- 5. Abnormal findings in the resting ECG at screening defined as:
  - a. QTcF> 450 or < 300 msec for men and QTcF> 470 or < 300 msec for women;
  - b. Notable resting bradycardia (HR < 45 bpm) or tachycardia (HR > 100 bpm);
  - c. Personal or family history of congenital long QT syndrome or sudden death;
  - d. ECG with QRS and/or T wave judged to be unfavourable for a consistently accurate QT measurement (e.g., neuromuscular artefact that cannot be readily eliminated, arrhythmias, indistinct QRS onset, low amplitude T wave, merged T- and U-waves, prominent U waves);

- e. Evidence of atrial fibrillation, atrial flutter, complete branch block, Wolf-Parkinson-White Syndrome, or cardiac pacemaker.
- 6. Use of any medications (prescription or over-the-counter [OTC]), within 14 days of study drug administration, or less than 5 half-lives (whichever is longer). Exceptions are paracetamol (up to 4 g/day) and ibuprofen (up to 1g/day), which are allowed up to 2 days before study drug administration and screening period. Other exceptions will only be made if the rationale is clearly documented by the investigator.

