- 7. Planned chemotherapy, hormonotherapy or radiotherapy within 1-week of the testing.
- 8. Diabetes mellitus, liver disease, kidney disease, hypo- or hyperthyroidism
- 9. Use of any vitamin, mineral, herbal, and dietary supplements within 7 days of study drug administration, or less than 5 half-lives (whichever is longer). Exceptions will only be made if the rationale is clearly documented by the investigator.
- 10. Participation in an investigational drug or device study (last dosing of previous study was within 90 days prior to first dosing of this study).
- 11. History of abuse of addictive substances (alcohol, illegal substances) or current use of more than 21 units (for males) or 14 units (for females) of alcohol per week, drug abuse, or regular user of sedatives, hypnotics, tranquilizers, or any other addictive agent
- 12. Positive test for drugs of abuse at screening or pre-dose.
- 13. Alcohol will not be allowed from at least 48 hours before screening or each admission.
- 14. Current use of tobacco or nicotine products and unable to abstain from use of these products within the previous 3 months before the first dose administration.
- 15. Is demonstrating excess in caffeine consumption (more than eight cups of coffee or equivalent per day).
- 16. Any confirmed significant allergic reactions (urticaria or anaphylaxis) against any drug, or multiple drug allergies (non-active hay fever is acceptable).
- 17. Loss or donation of blood over 500 mL within three months (males) or four months (females) prior to screening or intention to donate blood or blood products during the study.
- 18. If a woman, pregnant, or breast-feeding, or planning to become pregnant during the study.
- 19. Not willing to practice effective contraception during the study and not willing and able to continue contraception for at least 90 days after their last dose of study treatment.
- 20. Any known factor, condition, or disease that might interfere with treatment compliance, study conduct ECG or interpretation of the results such as drug or alcohol dependence or psychiatric disease.
- 21. Known hypersensitivity to the investigational drug or comparative drug or drugs of the same class, or any of their excipients.
- 22. Fitzpatrick skin type IV, V and VI, wide-spread acne, tattoos or scarring interfering with the area of interest (i.e., volar forearm).

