#### 2.8 OTHER TREATMENTS AND RESTRICTIONS

#### 2.8.1 Concomitant therapy

No prescription medications and OTC medications other than contraceptive medication will be permitted within 14 days prior to study drug administrations, or less than 5 half-lives (whichever is longer), and during the study. Exceptions are paracetamol (up to 4 g/day) and ibuprofen (up to 1g/day), which are allowed up to 2 days before all screening visits and 2 days before each study drug administration.

No vitamin, mineral, herbal, and dietary supplements will be permitted within 7 days prior to study drug administrations, or less than 5 half-lives (whichever is longer), and during the study.

Permitted medication(s)

Contraceptive medication.

Prohibited medication(s)

Paracetamol (up to 4 g/day) and ibuprofen (1 g/day) are not allowed within 2 days before screening and each study drug administration. Other exceptions will only be made if the rationale is clearly documented by the investigator.

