#### Laboratory assessments

Blood and other biological samples will be collected for the following clinical laboratory tests:

**Table 4.** Laboratory assessments

Lab	Tests	Collection & Analysis
Haematology	Haemoglobin [including Mean Corpuscular volume (MCV), Mean corpuscular haemoglobin (MCH), Mean corpuscular haemoglobin concentration (MCHC)], haematocrit, red cell count (RBC), total white cell count (WBC)and Platelet count. Differential blood count, including: basophils, eosinophils, neutrophils, lymphocytes, and monocytes.	2 mL of venous blood in a BD Vacutainer® K2EDTA tube. Samples will be analysed by the Clinical Chemistry Laboratory (AKCL) of Leiden University Medical Center (LUMC).
Chemistry and electrolytes	Sodium, potassium, calcium, inorganic phosphate, total protein, albumin, triglycerides, blood urea nitrogen (BUN), creatinine, uric acid, total bilirubin  , alkaline phosphatase, AST, ALT gamma-GT and LDH.	3.5 mL of venous blood in a BD Vacutainer® SST Gel and Clot Activator tube. Samples will be analysed by the AKCL of LUMC
Virology	HIV1 and HIV2 antigen and antibodies, Hepatitis B surface antigen, Hepatitis B antibodies and Hepatitis C antibodies	8.5 mL of venous blood in a BD Vacutainer® SSTGel and Clot Activator tube. Samples will be analysed by the Microbiology Laboratory (CKML) of the LUMC
Glucose	Glucose 	2 mL of venous blood in a BD Vacutainer® Sodium Fluoride tube. Samples will be analysed by the AKCL of LUMC
Urinalysis	Leucocytes, blood, nitrite, protein, urobilinogen, bilirubin, pH, specific gravity, ketones, glucose. If there is a clinically significant positive result, urine will be sent to the AKCL for microscopy and/or culture.	A midstream, clean-catch urine specimen will be analysed by dipstick (Multistix® 10 SG, Siemens Healthcare Diagnostics, Frimley, UK).
Pregnancy 	hCG. If there is a clinically significant, positive result, urine will be sent to the AKCL for confirmation.	A urine specimen will be analysed at CHDR by test kit (InstAlert, Innovacon, San Diego, USA).

Alcohol	Alcohol Breath Test	The hand-held Alco-Sensor IV meter (Honac, Apeldoorn, the Netherlands) will be used to measure the breath ethanol concentrations.
Urine drug screen	Cocaine, amphetamines, opiates (morphine), benzodiazepines and cannabinoids.	A urine specimen will be analysed at CHDR by test kit (InstAlert, Innovacon, San Diego, USA).

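### Inclusion 2 requires current opioid treatment, but exclusion 6 and section 2.8.1 prohibit it around dosing unless each patient has a documented exception, and no opioid-specific rule says which applies

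*Protocol*

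**What the plan says.** **Required.** Inclusion 2 (Protocol 2.6.2) asks for "Current treatment of their chronic pain with an opioidergic-acting drug (along with possible other drugs". It names no drug, dose, duration or stability period.

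**Prohibited.** Exclusion 6 (2.6.3) reads: "Use of any medications (prescription or over-the-counter [OTC]), within 14 days of study drug administration, or less than 5 half-lives". The longer of the two windows applies. Section 2.8.1 repeats the ban: "No prescription medications and OTC medications other than contraceptive medication will be permitted within 14 days prior to study drug administrations". The same sentence goes on to apply the half-life window where that is greater, and keeps the ban in force until the study ends. Its list of permitted medication contains only contraceptives. Paracetamol and ibuprofen have their own limited allowance.

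**Exceptions.** Both places carry the same clause: "Other exceptions will only be made if the rationale is clearly documented by the investigator". Neither mentions opioids.

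**Timing of checks.** The row "Inclusion and exclusion criteria" in Table 1 is marked at screening and again pre-dose. Section 2.3.2 also says that eligibility is checked repeatedly before dosing.

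**Drug screen.** Exclusion 12 is "Positive test for drugs of abuse at screening or pre-dose", with no exception of its own. The urine panel in Table 4 covers "Cocaine, amphetamines, opiates (morphine), benzodiazepines and cannabinoids". Table 1 schedules it at screening, on Day -1 and at follow-up.

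**The concern.** The drug that makes a patient eligible is also a drug that the medication rules remove. Moving the stop to the interval between screening and dosing does not clearly help. The criteria are applied again pre-dose, so on a literal reading current opioid treatment and no medication for 14 days are both demanded at the same check.

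Staff therefore cannot tell from the protocol whether to test a patient on or off the opioid, and two investigators could decide differently. Two things are at stake:

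- **Safety.** Section 2.2.2 itself warns that sudden discontinuation of an opioid can precipitate an abstinence syndrome. Section 2.3.2 notes that morphine above 3 mg can depress respiration in a dose-dependent manner.
- **Population.** Baseline pain thresholds and the response to morphine would be measured either in opioid-maintained patients or in patients taken off their opioid, or in an unplanned mixture of the two.

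**Working it through.** No sample size or power figure is involved. The check compares the rules and adds up the stated windows.

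**1. Rules side by side, for a patient on a prescribed opioid**

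| Rule | Opioid continued | Opioid stopped at least 14 days before dosing |
|---|---|---|
| Inclusion 2, at screening | met | met if stopped after screening |
| Inclusion 2, pre-dose | met | not met on a literal reading |
| Exclusion 6 and section 2.8.1 | breached unless an exception is documented | met if 14 days is the longer window |
| Exclusion 12, at screening | positive if the panel detects the opioid | same, if stopped after screening |
| Exclusion 12, Day -1 | positive if the panel detects the opioid | depends on clearance |

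Neither column satisfies every rule as written without an exception or an interpretation. Inclusion 2 applies to all 24 planned subjects, so all 24 need either a documented exception or a stop.

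**2. Time without the prescribed opioid, if it is stopped**

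Inputs: 14-day window (2.8.1); two treatments per subject and at least 7 days between periods (Synopsis, Trial Design); earliest follow-up 7 days after the last dose (2.5.1 and 2.5.3), or 14 - 2 = 12 days (Table 1).

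- Dose 1: 14 days
- Dose 2: 14 + 7 = 21 days
- Earliest follow-up: 21 + 7 = 28 days
- Earliest follow-up under Table 1: 21 + 12 = 33 days

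These are minima. They lengthen if 5 half-lives exceed 14 days, that is, for a half-life above 14 / 5 = 2.8 days. Sections 2.5.2 and 2.5.3 still refer to four occasions. On that wording the last dose would fall at 14 + 3 × 7 = 35 days and the earliest follow-up at 35 + 7 = 42. Two periods are used here because the Synopsis lists two treatments.

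This is time without the patient's own opioid. Each period still gives 3 + 7 = 10 mg of study morphine.

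**3. If the opioid is continued**

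The 3 mg and 7 mg boluses are added to a background opioid, with no rule on drug, dose, stability or sameness between periods. A patient whose background drug is morphine would also bring morphine and M6G into the pharmacokinetic endpoints. The amitriptyline study that section 2.3.2 cites as precedent did require a stable morphine dose over the preceding 2 days; this protocol has no counterpart.

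**The case against.** The strongest reply is that the exception clause resolves the matter. Inclusion 2 itself supplies the rationale, and a specific criterion can be taken to govern a general one. This has force: a reader might infer that no patient can be enrolled, and the documents do not support that. What remains is that a clause needed by every subject is working as the rule, yet it fixes no drug, dose or stability requirement.

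Other stronger readings also fail:

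- **That no washout is stated.** The 14-day or 5-half-life window is a general washout. What is missing is an opioid-specific rule on continuation, stable dose or taper.
- **That exclusion 12 bars everyone who meets inclusion 2.** The panel names opiates (morphine), and the documents do not say which other opioids it detects. Section 2.8.2 bars only a positive result that lacks an explanation, although it is written around illicit drugs and poppy seeds. The re-screening text in 2.5.1 allows another attempt when the reason for ineligibility is transient, besides retests for expected false positives. This conflict is partial.
- **That patients are opioid-free for 21 to 33 days.** They are not, because study morphine is given in each period.
- **That withdrawal is established for all 24.** Inclusion 2 gives no frequency, dose or duration of use, so the risk is plausible but not shown for each patient.
- **That exclusions 11 and 20 also bar prescribed opioid use.** This holds only by interpretation of their references to addictive agents and dependence.

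On the continuation route the protocol does have safeguards: saturation monitoring from 2 h to the end of Day 1 (Table 1 notes), naloxone and emergency care within 5 minutes (2.3.1), and medical supervision with discharge by a physician (2.3.2). They lessen the risk of added morphine but do not remove it.

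**Conclusion.** The conflict between inclusion 2 and exclusion 6 with section 2.8.1 is in the current text and should be settled before screening. It touches all 24 planned subjects. Exclusion 12 is a secondary conflict whose reach among the 24 cannot be determined from the protocol.

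The 14, 21 and 28 (or 33) day figures rest on three assumptions: the opioid is stopped, there are two periods at the minimum spacing, and 14 days is the longer window.

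A reader might go on to infer that the morphine plus nortriptyline versus morphine contrast is biased. That is not shown: each subject is their own control, and any added variance cannot be quantified from the documents. The case rests on patient safety, workable eligibility and a defined population.

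**What to change.** Amend the eligibility and concomitant-medication text before screening starts:

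1. Keep inclusion 2. Require a stable dose of the prescribed opioid and of a listed set of permitted co-analgesics, the same in both periods of a subject.
2. Exempt these explicitly from exclusion 6, section 2.8.1 and exclusion 12, so that a positive opiate screen explained by the recorded prescription does not exclude.
3. State that prescribed use alone does not trigger exclusion 11 or 20, and keep exclusion 20 for dependence.
4. Do not allow morphine as the background opioid, or else state a rule for measurable pre-dose morphine or M6G.
5. Do not allow background nortriptyline or another tricyclic. It would be present in both periods and could dilute the only planned contrast.
6. Set a maximum background opioid dose.

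The cost is one text amendment with no new assessments. The drawback is that IV morphine is deliberately given on top of a background opioid, hence the dose ceiling.

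If the sponsor instead intends a washout, inclusion 2 must be reworded to prior opioid treatment, a supervised taper with withdrawal monitoring written in, and the screening opiate test aligned with it. That costs more and leaves patients without their prescribed opioid for at least 28 days. The choice between the two is clinical.

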#### 2.6.3 Exclusion criteria

- Evidence of any active or chronic disease or condition that could interfere with, or for which the
  treatment of might interfere with, the conduct of the study, or that would pose an unacceptable
  risk to the subject in the opinion of the investigator (following a detailed medical history, physical
  examination, vital signs (systolic and diastolic blood pressure, pulse rate, body temperature) and
  12-lead electrocardiogram (ECG)). Minor deviations from the normal range may be accepted, if
  judged by the Investigator to have no clinical relevance.
- 2. Clinically significant abnormalities, as judged by the investigator, in laboratory test results (including hepatic and renal panels, complete blood count, chemistry panel and urinalysis). In the case of uncertain or questionable results, tests performed during screening may be repeated before randomization to confirm eligibility or judged to be clinically irrelevant for patient with chronic neuropathic pains.
- 3. Positive Hepatitis B surface antigen (HBsAg), Hepatitis C antibody (HCV Ab), or human immunodeficiency virus antibody (HIV Ab) at screening.
- 4. Systolic blood pressure (SBP) greater than 140 or less than 90 mm Hg, and diastolic blood pressure (DBP) greater than 90 or less than 50 mm Hg at screening.
- 5. Abnormal findings in the resting ECG at screening defined as:
  - a. QTcF> 450 or < 300 msec for men and QTcF> 470 or < 300 msec for women;
  - b. Notable resting bradycardia (HR < 45 bpm) or tachycardia (HR > 100 bpm);
  - c. Personal or family history of congenital long QT syndrome or sudden death;
  - d. ECG with QRS and/or T wave judged to be unfavourable for a consistently accurate QT measurement (e.g., neuromuscular artefact that cannot be readily eliminated, arrhythmias, indistinct QRS onset, low amplitude T wave, merged T- and U-waves, prominent U waves);

- e. Evidence of atrial fibrillation, atrial flutter, complete branch block, Wolf-Parkinson-White Syndrome, or cardiac pacemaker.
- 6. Use of any medications (prescription or over-the-counter [OTC]), within 14 days of study drug administration, or less than 5 half-lives (whichever is longer). Exceptions are paracetamol (up to 4 g/day) and ibuprofen (up to 1g/day), which are allowed up to 2 days before study drug administration and screening period. Other exceptions will only be made if the rationale is clearly documented by the investigator.
- 7. Planned chemotherapy, hormonotherapy or radiotherapy within 1-week of the testing.
- 8. Diabetes mellitus, liver disease, kidney disease, hypo- or hyperthyroidism
- 9. Use of any vitamin, mineral, herbal, and dietary supplements within 7 days of study drug administration, or less than 5 half-lives (whichever is longer). Exceptions will only be made if the rationale is clearly documented by the investigator.
- 10. Participation in an investigational drug or device study (last dosing of previous study was within 90 days prior to first dosing of this study).
- 11. History of abuse of addictive substances (alcohol, illegal substances) or current use of more than 21 units (for males) or 14 units (for females) of alcohol per week, drug abuse, or regular user of sedatives, hypnotics, tranquilizers, or any other addictive agent
- 12. Positive test for drugs of abuse at screening or pre-dose.
- 13. Alcohol will not be allowed from at least 48 hours before screening or each admission.
- 14. Current use of tobacco or nicotine products and unable to abstain from use of these products within the previous 3 months before the first dose administration.
- 15. Is demonstrating excess in caffeine consumption (more than eight cups of coffee or equivalent per day).
- 16. Any confirmed significant allergic reactions (urticaria or anaphylaxis) against any drug, or multiple drug allergies (non-active hay fever is acceptable).
- 17. Loss or donation of blood over 500 mL within three months (males) or four months (females) prior to screening or intention to donate blood or blood products during the study.
- 18. If a woman, pregnant, or breast-feeding, or planning to become pregnant during the study.
- 19. Not willing to practice effective contraception during the study and not willing and able to continue contraception for at least 90 days after their last dose of study treatment.
- 20. Any known factor, condition, or disease that might interfere with treatment compliance, study conduct ECG or interpretation of the results such as drug or alcohol dependence or psychiatric disease.
- 21. Known hypersensitivity to the investigational drug or comparative drug or drugs of the same class, or any of their excipients.
- 22. Fitzpatrick skin type IV, V and VI, wide-spread acne, tattoos or scarring interfering with the area of interest (i.e., volar forearm).
- 23. Any current, clinically significant, known medical condition in particular any existing conditions that could have affected sensitivity to cold (such as atherosclerosis, Raynaud's disease, urticaria, hypothyroidism) or pain (paraesthesia, etc.).
- 24. Subjects who indicated nociceptive tests intolerable at screening or who achieved tolerance at >80% of maximum input intensity for the cold pressor or electrical pain tasks.

